5.3. Enrollment

After completing the informed consent, the final screening check takes place during the angiography: this will be confirmed and documented. Only once the below criteria are fulfilled can the patient be considered enrolled in the study:

All angiographic inclusion and exclusion criteria outlined in section 4.2 are fulfilled.

For the purposes of this clinical study, patients will be considered subjects after enrollment has been confirmed.

If a patient has provided informed consent but has not met one of the above criteria for enrollment inclusion into the study, he/she will be considered a screen failure.

5.4. Baseline Assessment

Prior to treatment, each patient's medical history and demographics will be collected. Preoperative procedures include a physical examination, documentation of disease, relevant medical history and medication or coronary intervention.

Furthermore, the subject must complete a series of assessments at the time preceding index treatment. These assessments include:

- Laboratory Tests – full blood count, serum creatinine, cardiac troponin (cTn), HbA1c, and lipid profile (non-fasting acceptable).
- Pregnancy test (β HCG subunit) - to be performed for women of childbearing potential if the last Menstrual Period does not fall within the last 10 days.
- If it is not possible to perform the pregnancy test for women of childbearing potential in urgent cases, such patients will not be included in the study.

5.5. Pre-Procedure

Beyond the anti-platelet regimen, patients are to be medicated as per institutional procedures. All anti-platelet and oral medication administered will be captured in the medical notes for subsequent capture in the electronic case report form (eCRF).

5.6. Procedure Visit

5.6.1. Index Procedure

Angiography, calcium modification techniques and HD IVUS imaging will be performed according to current international guidelines.

Once the decision to proceed to PCI is made, prior to guidewire insertion, all patients will be administered heparin or bivalirudin according to the standard practice. All patients undergoing PCI will receive a loading dose of an ADP receptor antagonist. Patients not already receiving aspirin will be treated with an oral or intravenous loading dose of aspirin.

After intracoronary injection of nitroglycerin, baseline angiography of the target vessel (TV) will be performed where single worst projection will be recorded for QCA analysis showing the target lesion (TL) for all subjects.

5.6.2. Intravascular ultrasound (IVUS)

Intravascular imaging of the lesion will then be performed using HD 60 MHz IVUS. Standard HD IVUS procedures should be followed as per the product manufacturer guideline during each HD IVUS recording. Automated pullback must be performed to image the full extent of the lesion from at least 10mm distal to the distal edge of the lesion to at least 10mm proximal to the

proximal edge of the lesion for each recording. A pullback speed of 0.5-1mm/s should be used. Longitudinal and cross-sectional planes must be recorded for each recording.

The first, baseline HD IVUS recording will take place after the guidewire has crossed the lesion. This will allow for determination of baseline lesion characteristics, which can be input into the calcium modification algorithm. The characteristics that are to be assessed for the calcium modification algorithm include the degree of calcium arc, the lesion length, the reference vessel diameter, and the presence/absence of nodular calcium. The individual operator will make their assessment of the target lesion calcium characteristics and proceed to use the calcium modification algorithm (Section 5.6.3). The operator will then implement the lesion preparation method recommended by the calcium modification algorithm.

Once the recommended calcium modification and lesion preparation has been completed, a second HD IVUS imaging recording will be performed using the same protocol as the baseline HD IVUS recording. This post lesion preparation HD IVUS recording will assess for calcium fractures and for luminal gain as compared to the baseline HD IVUS recording. The lesion characteristics assessed by the operator will be input to the next stage of the calcium modification algorithm, which will provide the next recommended action.

If the individual operator is satisfied that optimal lesion preparation has been achieved by the presence of calcium fractures or acceptable luminal gain (or at the clinical discretion of the operator), they can proceed to treat the lesion with bioabsorbable polymer everolimus eluting stent(s). The operator may use their own clinical judgement to choose the appropriate stent type for the individual patient and lesion characteristics. If optimal lesion preparation has not been achieved by the above criteria, then further lesion preparation is recommended by the calcium modification algorithm. Each time that further calcium modification is performed, an additional HD IVUS recording is required to assess for optimal lesion preparation. Once optimal lesion preparation is achieved, the operator will then proceed to stent insertion. Pre-dilatation and post-dilatation may be performed by the operator as per their usual practice. Should the operator opt to avoid stent insertion during the index procedure based on their clinical decision, no further HD IVUS recordings will be required at this time point. Should a staged procedure be planned, and a stent inserted later, the final result should be assessed with HD IVUS, and recordings uploaded to the eCRF.

Following stent insertion, a third and final HD IVUS recording of the target lesion will be performed. If additional stent optimization, such as with further post-dilatation with non-compliant angioplasty balloon is required, this is permitted and must be followed by another HD IVUS recording such that the final HD IVUS recording shows the final optimized result. The baseline HD IVUS, the post lesion preparation HD IVUS (single or multiple runs) and the final HD IVUS recorded images must be uploaded to the eCRF for core lab analysis.

5.6.3. *Calcium modification protocol*

CYCLOPES treatment algorithm

**Set
Up**

1. Cross the calcified lesion(s) with a coronary guidewire
2. Pass the imaging catheter through the lesion
3. If the imaging catheter does not pass, pre-dilate with angioplasty balloon(s) and re-attempt
4. For balloon uncrossable lesions, up-front rotational/orbital atherectomy may be required

Define: potential imaging findings identified on IVUS

Circumferential
Calcium

Long segment
calcification

Vessel sizing and
RVD*

Wire bias

Nodule

Reverberations

Modify: proposed strategies based on IVUS findings

Attempt 1:1 NC Balloon or cutting balloon† dilatation as first step.

If complete balloon expansion is achieved, additional calcium modification may not be necessary, so proceed to the **Confirm** step. Multiple balloons may be used at the discretion of the operator.

If angiographic complete balloon expansion is not achieved, additional modification strategies are suggested below based on IVUS characteristics‡

Rotational Atherectomy (with Burr size approx. 0.5 x mean RVD):

Ideal calcium characteristics: Balloon uncrossable lesions, concentric or eccentric lesions with small MLD, long calcific lesions (>20 mm length), nodular calcium

Intravascular Lithotripsy (with balloon size approx. 1.0 x mean RVD):

Ideal calcium characteristics: Concentric calcium (arc >270°), esp. if large MLD
IVL may also be considered in eccentric or nodular calcium esp. if unfavourable wire bias

Confirm: modified calcium and optimal stent criteria

Signs of calcium modification

Increased
reverberations

Calcium
fractures

IVUS optimal stent implantation criteria

- ≥ 80% stent expansion
- Complete stent apposition
- No edge dissection
- Full lesion coverage with <50% plaque burden at proximal and distal references

Co-primary end points

- MSA at area of maximal calcification
- MACE at 1 year

Key secondary end points

- MSA at end of index procedure
- MSA/vessel area at MSA, %

Signs of calcium modification present:
Stent insertion and optimization

Then repeat IVUS post stent optimization and insertion

Signs of calcium modification absent:
Return to modify

* Refer to the IVUS 1 2 3 Essentials Pre-stent Workflow.

† Cutting balloon size should be chosen as 0.5mm smaller than RVD (media-to-media measurement) of the vessel size as determined by intravascular imaging. It is strongly recommended that cutting balloon therapy be delivered to the target lesion at high pressure (e.g., 18-20 atmospheres) as this has been shown to be safe and effective in prior studies.

‡ Calcium morphology may be heterogenous, device selection at operator discretion.

Figure 2 The CYCLOPES calcium modification algorithm provides a systematic approach to selection of the appropriate calcium modification device.

The CYCLOPES calcium modification algorithm illustrated in Figure 2 offers a 3-step process for the management of coronary calcification “Define, Modify, Confirm” (DMC). The algorithm is guided by intravascular ultrasound to be performed with mechanical pullback, using HD IVUS. The IVUS 1, 2, 3 Essentials Workflow should be performed at each HD IVUS acquisition throughout the algorithm[12].

CYCLOPES treatment algorithm

[figure not shown]
[figure not shown]
[figure not shown]
Pre Stent Workflow			
Adapted from IVUS 1 2 3 Essentials			
Landing zone	No disease or minimal plaque burden	Mild or moderate plaque burden $\leq 50\%$	Heavy plaque burden $\geq 50\%$ plaque burden
Measurements	 Lumen-Lumen and EEL-EEL show minimal difference	 Lumen-Lumen and EEL-EEL differ by $\geq 1\text{mm}$	 Lumen-Lumen and EEL-EEL differ substantially
Distal edge stent diameter	Size stent to L-L measurement to minimize risk of edge dissection	Size stent to L-L measurement to minimize risk of edge dissection	This is not an appropriate landing zone for a stent – seek less diseased segment
Proximal or distal postdilation balloon diameter	Size postdilation balloon to EEL but do not exceed EEL-EEL measurement	Size postdilation balloon to EEL. Downsize by 0.5mm or aim to size half way between lumen and EEL	Postdilation balloon should not be sized to EEL-EEL measurements in areas of heavy plaque burden. Balloons are likely to be oversized due to positive remodelling.

Figure 3 Pre-stent workflow based on IVUS 123 Essentials workflow

Having met the eligibility criteria outlined in section 4.2, including QCA assessment, the set-up step is initiated. This involves crossing the calcified lesion with a coronary guidewire and attempting to cross the lesion with the imaging (IVUS) catheter. If the imaging catheter does not pass through the lesion, the lesion should be predilated with an angioplasty balloon to facilitate crossing the lesion with the imaging catheter at a second attempt. For any lesions that are not crossable with an angioplasty balloon, an upfront rotational/orbital atherectomy strategy may be required to proceed.

Once the IVUS catheter is passed distal to the lesion, the first step of the DMC process, “Define” is initiated. The first HD IVUS acquisition takes place to define the potential characteristics of coronary calcification seen with intravascular imaging. The six features to assess are circumferential calcium, long segment of calcification, vessel sizing and reference vessel diameter (RVD), wire bias, calcific nodule, and reverberations. Circumferential calcium refers to the presence or absence of circumferential calcium. A long segment of calcification is assessed by the operator as a segment of calcified disease >20mm. Vessel sizing and reference vessel diameter (RVD) is assessed and recorded by the operator using the IVUS 123 Essentials workflow method [13]. Wire bias is defined as wire bias towards calcium or away from calcium. Calcific nodule refers to the presence or absence of a calcified nodule on HD IVUS. Reverberations refer to the presence of reverberations seen on HD IVUS.

Once the lesion has been defined, move to the “Modify” step. The first part of this step involves attempting to pre-dilate the lesion with a non-compliant balloon or cutting balloon. For non-compliant balloon dilatation, ideally a balloon sized in a 1:1 ratio to the reference vessel diameter as assessed by HD IVUS. For cutting balloon dilatation, the cutting balloon size should be chosen as 0.5mm smaller than media-to-media measurement of the vessel size as determined by intravascular imaging. It is strongly recommended that cutting balloon therapy be delivered to the target lesion at high pressure (e.g., ~18-20 atmospheres) as this has been shown to be safe and effective in prior studies[1].

If 1:1 balloon expansion is achieved with angiographic evidence of complete balloon expansion, then the lesion may be sufficiently prepared and additional calcium modification may not be required, so proceed to step 3, “Confirm”. If there is incomplete balloon expansion, then additional calcium modification methods may be required. Using the characteristics assessed with HD IVUS in the “Define” step, choose an additional modality for calcium modification. It is important to note that calcium characteristics may be heterogenous, as such, the final choice of calcium modification modality is at the discretion of the operator.

Ideal calcium characteristics for rotational atherectomy include balloon uncrossable lesions and long calcific lesions and calcified nodules, particularly if the wire is biased towards the nodule. Burr size should be approximately 0.5 x mean RVD.

Ideal calcium characteristics for intravascular lithotripsy include the presence of a calcium arc >270° in large vessels. IVL may also be considered for eccentric or nodular calcium where wire is biased away from the nodule.

Once the chosen modality for calcium modification has been used, move to the “Confirm” step, which involves post calcium modification HD IVUS imaging to assess the outcome of the “Modify” step. If signs of calcium modification are present, defined as the presence of calcium fractures or increased reverberations visualized on HD IVUS, then the algorithm directs the operator to DES insertion and optimization. Following DES insertion and optimization, a final HD IVUS acquisition takes place to assess the optimal stent implantation criteria. These criteria include at least 80% stent expansion, complete stent apposition, no edge dissection and full lesion coverage with less than 50% plaque burden at proximal and distal references.

Further post-dilatation for DES optimization may be required at this point if the optimal stent implantation criteria is not met. This should be performed at the operator’s discretion. If additional DES optimization is performed, a final HD IVUS acquisition should be obtained showing the result.

If at the “Confirm” step signs of calcium modification are absent, then the algorithm re-directs back to the modify step. At this point the choice of calcium modification modality is at the discretion of the operator. Multiple modalities may be used. The “Confirm” step must be completed after repeating the “Modify” step.

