Design:	
CYCLOPES is a prospective, multicenter, open-label, single arm trial assessing the feasibility and efficacy of an intracoronary ultrasound guided algorithm (Figure 1) for calcium modification in patients undergoing percutaneous coronary intervention (PCI) for chronic calcific coronary artery disease. The study will enroll 500 patients who will undergo PCI with calcium modification.
 
Participants will be enrolled prospectively in 25 sites in Ireland, Switzerland, the United Kingdom, Spain, France, Italy and Germany (7 countries).
 
All patients will have coronary angiography (QCA) and intravascular ultrasound (IVUS) imaging with 60MHz HD IVUS of the calcified lesion at baseline. The lesion will be characterized based on calcium distribution and morphology as assessed by HD IVUS. Depending on the specific lesion characteristics, the appropriate method for calcium modification will be chosen and performed in line with the CYCLOPES calcium modification algorithm included in the study protocol.
 
The calcific lesion will be imaged for a second time by 60MHz HD IVUS following calcium modification. The operator will then proceed, if no further lesion preparation is required, to deploy a bioabsorbable polymer Everolimus eluting stent using standard stenting techniques, post dilatation will be performed at the operator's discretion. The treated lesion will be assessed again using intravascular ultrasound following stent deployment and optimization.

	
The primary end points will be the post stenting minimal stent area (MSA) at the site of maximum calcification relative to reference lumen area assessed with 60MHz HD IVUS and target lesion failure (TLF) at 1-year post-procedure. All HD IVUS determined endpoints will be assessed at an independent imaging core laboratory.
 
Participants will be assessed with clinic or phone visits at hospital discharge, 1 month and 12-month time points post procedure.

Objectives:	The aim of this study is to validate a comprehensive and intravascular imaging-based calcium modification algorithm for the treatment of moderate to severely calcified coronary lesions.

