Medical history	x			
Physical examination	x			(x)
Cardiac enzymes ²	x	x		
Review of laboratory data ³ , ECG	x	x		(x)
Review of concomitant medications	x	x	x	x
Coronary angiography and PCI (with 60 MHz HD IVUS guidance and use of calcium modification devices according to a specific algorithm) ⁴	x			
Adverse event assessment/reporting		x	x	x
Assessment of endpoints		x	x	x
Final status				x

¹ Follow-up assessments may consist of a structured telephone interview, or if standard of care, an office visit. ² High sensitivity troponin is mandatory for pre-index procedure, 18-24 hours post-index procedure (or at immediately prior to discharge, if discharged before 18 hours post-procedure) and in case of a clinical event; ³ Full blood count, serum creatinine, HbA1c, lipid profile (non-fasting acceptable). ⁴ For all subjects, coronary angiography and raw 60 MHz HD IVUS image recordings from 3 specified time points (baseline, post lesion preparation and post stent insertion) will be sent to the independent Imaging Core Laboratory for evaluation of primary endpoint (MSA). ⁵ One post-procedural 12 lead ECG should be performed prior to hospital discharge. A repeat 12 lead ECG may be performed if clinically indicated.

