3.3. Endpoints

3.3.1. Co-Primary Endpoint

1. Minimum stent area (MSA) at the site of maximum calcification at the end of the index procedure
2. Target lesion failure (TLF) (cardiovascular death, non-fatal myocardial infarction related to the target vessel, unplanned ischemia-driven target lesion revascularization) at 1 year

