The TL is the portion of the coronary artery that was in immediate contact with the DCB plus a margin of 5 mm on both ends.

TARGET VESSEL (TV)

The TV is defined as the index coronary artery which was in physical contact with any component (guiding catheter, guide wire, balloon catheter, etc.) of the angioplasty hardware during the initial procedure.

TARGET LESION FAILURE (TLF)

(ARC 2 definition)

Cardiovascular death, target-vessel myocardial infarction, or clinically driven target-lesion revascularization.

TARGET VESSEL FAILURE (TVF)

(ARC 2 definition)

Cardiovascular death, target-vessel myocardial infarction, driven target-vessel revascularization

TARGET LESION REVASCULARIZATION (TLR)

Defined as any repeat percutaneous intervention of the TL or bypass surgery of the target vessel.

Clinically driven revascularizations are those in which the patient has a positive functional study, ischemic ECG changes at rest in a distribution consistent with the target vessel, or ischemic symptoms. Revascularization of a TL with an in-lesion diameter stenosis $\geq 70\%$ (by QCA) in the absence of the above-mentioned ischemic signs or symptoms is also considered clinically driven. In the absence of QCA data for relevant follow-up angiograms, the clinical need for revascularization is adjudicated using the presence or absence of ischemic signs and symptoms.

Non-clinically driven repeat target lesion revascularizations are those in which the patient undergoes a non-emergent revascularization for a diameter stenosis $< 50\%$ (by QCA). Non-emergent repeat target lesion revascularization for a diameter stenosis $< 70\%$ (by QCA) in patients without either a positive functional study or angina are also considered non-clinically driven defined as any repeat revascularization of the target site whether by PCI or bypass surgery.

TARGET VESSEL REVASCULARIZATION (TVR)

Any target vessel revascularization, death, or MI attributed to the target vessel.

TIMI CLASSIFICATION

TIMI 0	No perfusion.
TIMI 1	Penetration with minimal perfusion. Contrast fails to opacify the entire bed distal to the stenosis for the duration of the cine run.
TIMI 2	Partial perfusion. Contrast opacifies the entire coronary bed distal to the stenosis. However, the rate of entry and/or clearance is slower in the

coronary bed distal to the obstruction than in comparable areas not perfused by the dilated vessel.

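### Planned staged stenting is allowed, but the protocol contradicts itself on whether the staged recording supplies the MSA, and its TLR and TVR definitions make no exception for it

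*Protocol*

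**What the plan says.** Section 5.6.2 allows two departures from stenting at the index session. The first is deferral, with the imaging requirement lifted for that session: "Should the operator opt to avoid stent insertion during the index procedure based on their clinical decision, no further HD IVUS recordings will be required". The second is staging: "Should a staged procedure be planned, and a stent inserted later, the final result should be assessed with HD IVUS", and that recording is to be uploaded to the eCRF.

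On MSA, section 3.3.1 names the co-primary as "Minimum stent area (MSA) at the site of maximum calcification at the end of the index procedure". The synopsis endpoint list, section 3.1 and section 8.3.3 give the same timing, and secondary endpoint 2 in section 3.3.2 is also tied to the end of the index procedure. Other places differ. The synopsis design text reads "The primary end points will be the post stenting minimal stent area (MSA) at the site of maximum calcification relative to reference lumen area". Table 1, footnote 4, lists three recording time points, the last being "post stent insertion) will be sent to the independent Imaging Core Laboratory for evaluation of primary endpoint (MSA". Figure 2 in section 5.6.3 lists the co-primary MSA with no timing at all.

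On revascularization, section 3.3.2 lists TVR (endpoint 4) and TLR (endpoint 5) without qualifiers. Appendix A gives TLR as "Defined as any repeat percutaneous intervention of the TL or bypass surgery of the target vessel", and TVR as any revascularization of the target vessel, together with attributed death or MI. Neither mentions planned staging. The co-primary TLF in sections 3.3.1 and 8.3.3 counts only "unplanned ischemia-driven target lesion revascularization". The Appendix A entry for TLF asks instead for a clinically driven TLR and does not require it to be unplanned.

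**The concern.** A patient whose lesion is modified at the index session and stented by plan at a second session has been treated within the protocol. Two endpoint rules do not fit that patient.

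First, at the end of the index procedure there is no stent to measure. Read literally, the endpoint list leaves out a recording that the protocol itself asks the site to make and upload. Read with the synopsis design text and Table 1, the same recording is the endpoint. These readings give different denominators for a co-primary endpoint, and nothing in the protocol chooses between them.

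Second, secondary TLR and TVR would count the planned completion of treatment as an event. The study tests no hypothesis (section 8.3.1), so the reported rates and summaries are its result. An event count that mixes completions with failures would be misread as poor lesion durability.

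**Working it through.** The protocol states no deferral rate, event rate or MSA spread, so there is no figure of its own to reproduce. The check is a comparison of definitions, followed by an illustration.

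**1. MSA.** Section 5.6.2 separates the index procedure from the later staged one. Appendix A starts a PCI procedure when the guidewire crosses the first lesion, so a later session is most naturally a new procedure. End-of-index timing (synopsis endpoints, 3.1, 3.3.1, 3.3.2, 8.3.3) then excludes the staged recording. Post-stenting timing (synopsis design, Table 1) includes it. No section says which governs. Section 8.2 adds a further gap: the FAS requires a completed index procedure, without saying whether a session that ends unstented is complete.

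**2. TLR and TVR.** The index session already includes percutaneous treatment of the lesion, so a later stent is a second percutaneous intervention on it and fits the Appendix A wording of TLR. It also fits the TVR wording.

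**3. Co-primary TLF.** A planned procedure is not unplanned, so under 3.3.1 and 8.3.3 it is not an event. Under Appendix A, ischemic symptoms, a positive functional study or a QCA stenosis of at least 70% makes a revascularization clinically driven. Section 4.2.1 enrolls patients for symptoms or documented ischaemia, so a staged stenting could qualify under that text.

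**4. Illustration.** The document supplies N = 500 (section 8.4). Assumed: share staged s, true any-TLR rate p = 4%, every staged patient later stented, and a mean MSA deficit d = 1 mm² in staged lesions.

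- Patients without an end-of-index MSA: 500 × s
- TLR counted literally, no overlap with true events: p + s
- TLR counted literally, independent overlap: p + s(1 − p)
- Rise in mean MSA if staged lesions are dropped: s × d

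| s | No index MSA | MSA available | p + s | p + s(1 − p) | MSA shift |
|---|---|---|---|---|---|
| 2% | 10 | 490 | 6% | 5.9% | 0.02 mm² |
| 5% | 25 | 475 | 9% | 8.8% | 0.05 mm² |
| 10% | 50 | 450 | 14% | 13.6% | 0.10 mm² |

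**5. Sensitivity to the assumed rate.** With p = 5% and overlap allowed, counts rounded and exact 95% intervals:

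- true rate: 25/500 = 5.0% (3.26 to 7.29)
- 2% staged: 35/500 = 7.0% (4.92 to 9.60)
- 5% staged: 49/500 = 9.8% (7.34 to 12.75)
- 10% staged: 73/500 = 14.6% (11.62 to 18.00)

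At 5% staged, the literal interval already lies wholly above the interval for the true rate. If staged completions are excluded, the rate returns to 5.0%. If staged recordings are accepted, MSA is available for all 500, provided all are analysable.

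**The case against.** The strongest reply is that the protocol intends the sensible result. The staged recording is required, Table 1 sends the post-stent recording to the core laboratory for the primary endpoint, and section 11.5 calls for post-PCI analysis in all subjects. A reader might infer from 3.3.1 alone that staged patients lose their MSA. The documents do not support that: the data are collected, and what is missing is a rule assigning them. The contradiction remains, because the formal endpoint list and the primary analysis section carry the opposing text.

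On TLR, one can argue that completing a planned treatment is not a repeat, and that section 14.3 leaves classification to a CEC charter that is not shown. The charter may settle it. It should not have to override an Appendix A definition that has no exception.

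A reader might also infer that staging inflates the co-primary TLF. Sections 3.3.1 and 8.3.3 exclude planned procedures, so it does not. The only exposure is through the conflicting Appendix A entry.

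Three further inferences go too far:

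- That deferral selects the hardest lesions and so flatters MSA is plausible but stated nowhere. Section 5.6.2 refers only to the operator's clinical decision, and section 5.6.3 sends unmodified lesions back for more modification.
- The non-missing denominator rule in 8.3.1 concerns percentages, not a continuous MSA. The relevant text is the no-imputation rule there, which defers to the SAP and which section 8.5 contradicts.
- Strategy success carries no index timing, so staged stent delivery is not excluded from it.

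**Conclusion.** The concern holds as a conflict of definitions. For planned staged stenting, the protocol gives incompatible timings for the co-primary MSA; on the literal endpoint wording, a measurement it collects falls outside the endpoint. Secondary endpoints 4 and 5, as defined, would count planned completion as an event. Co-primary TLF is unaffected under 3.3.1 and 8.3.3, but Appendix A does not agree with them.

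The size depends on a deferral rate that the protocol does not state. With 2% to 10% staged and a true TLR of 4%, all assumed, secondary TLR would read about 6% to 14%. The effect on mean MSA is probably small: 0.05 mm² at 5% staged even if those lesions average 1 mm² less, which is also an assumption. If staging is very rare, both effects nearly vanish, though the contradiction in the text remains.

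**What to change.** - In 3.3.1, 3.3.2 and 8.3.3, and in the matching synopsis and section 3.1 text, time MSA at the end of the final planned stenting procedure of the target lesion. That is either the index procedure or a staged procedure declared in the eCRF at the end of the index procedure.
- Report the number of patients never stented beside the MSA summary.
- In Appendix A, exclude staged completion of the target lesion, if so declared, from TLR and TVR.
- Align the Appendix A TLF entry with the unplanned, ischemia-driven wording of 3.3.1.
- Keep the TLF clock at the index procedure.

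Declaration at the end of the index session matters, because it stops a later failure from being relabelled as a planned stage.

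The cost is a wording amendment and one eCRF field. The staged recording is already required, so no new imaging is needed. The drawback is that MSA for some patients is measured later than the index date. The change concerns endpoint accounting only and leaves the choice of when to stent as the protocol has it.
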